6.3 Baseline PSG visit*

Conventional In-lab Overnight Polysomnography (PSG): Procedures and scoring will follow the latest American Academy of Sleep Medicine Scoring Rules.²⁸ Standard measures will include: total sleep time (TST), sleep efficiency, sleep latency (SL [minutes from lights out to first 30 seconds of any sleep stage]), wake after sleep onset, total arousal index (TAI, average number of EEG arousals per hour of sleep), % total sleep time spent in stage 1, 2, 3, and REM sleep, the Respiratory Disturbance Index (RDI - total number of apneas, hypopneas and respiratory-related arousals per hour of sleep) central apnea index (total number of central apneas per hour of sleep), oxygen desaturation index (ODI, number of desaturation events $\geq 3\%$ below baseline oxygen saturation levels), minimum oxygen saturation (Min O₂), and % of sleep time with O₂ saturation $\leq 88\%$. PSG's will be scored by a single, experienced, technologist, masked to treatment group. Scoring will be reviewed and confirmed, and studies interpreted, by a board-certified sleep specialist.

Innovative PSG Signal Analysis Algorithms: In addition to conventional PSG measures, PSG data will also be analyzed using a novel PSG algorithm that has never been applied to sleep or cognitive research in MS patients. **This will involve no changes to the subject's overnight PSG procedure or experience.** This novel method, invented and patented by co-investigators Drs. [name] and [name],^{29, 30} uses variations in EEG power (for specific frequency bands) during discrete phases of the respiratory cycle (early expiration, late expiration, early inspiration, and late inspiration) to detect subtle, cortical microarousals not visible on standard visual inspection of the PSG.²⁸⁻³⁰ This algorithm will allow a more sensitive evaluation of potential effects that disordered nocturnal respiration could have on cerebral cortical function among MS patients. Specifically, respiratory cycle-related EEG changes (RCREC), which reflect cortical microarousals, will be computed to detect subtle disturbances in respiration beyond standard apnea/hypopnea measures, which will then be correlated with MACFIMS scores.

The study team has also pioneered the application of analyses of sleep dynamics – temporal patterns of sleep stages rather than simpler total sums or percentages of stage 1, 2, 3, and REM sleep – to discriminate between disordered and normal sleep when standard measures fail to do so. These techniques also will be applied to sleep recordings, to identify additional sleep-related predictors of cognitive dysfunction beyond conventional measures of nocturnal respiration in MS patients.

*For subjects who have a recent diagnosis of OSA based on recent (within 1 year) clinical University of Michigan Sleep Laboratory PSG, these clinical PSG data will be used for the same baseline analyses above.

6.4 Randomization

Randomization Process/Blinding: Subjects who meet criteria for OSA on baseline or clinical PSG (n~140, anticipated) will be randomized (2:1 randomization) to determine whether they will receive expedited PAP therapy (Group 1, n~93), or standard of care PAP therapy (Group 2, n~47). Computer-based randomization will be stratified by sleep apnea severity (RDI $<$ or ≥ 30) to minimize imbalances in apnea severity between groups. PSG technicians, PSG interpreters, and study staff who conduct and score neuropsychological tests will remain blinded to group allocation for the duration of the study. The subject, PI, co-investigators, coordinators, and statistician will not be blinded. **Subjects will be contacted with the randomization**

assignment that determines whether they will be scheduled for immediate PAP titration (Group 1) or delayed PAP titration after their month 3 cognitive testing.

6.5 PAP titration

(After randomization for Group 1, and following month 3 cognitive testing for Group 2)

Standard AASM guidelines will be followed in laboratory-based PAP titration studies designed to determine effective continuous PAP (CPAP) or bilevel PAP (BiPAP) settings, when necessary, for subjects with OSA. Studies will be scored by certified PSG technologists and interpreted by a board-certified sleep physician. Clinicians involved in the study or the subject's treating sleep provider will then place an order for PAP equipment at appropriate settings with a local durable medical equipment (DME) provider. DME will be covered by the subject's insurance. The DME company will provide subjects with equipment, instruct them on proper use at home, and provide supplies as needed. PAP titrations can be waived if subjects have had a recent U-M sleep lab clinical PAP titration within the past year. In cases where AutoPAP is recommended by the participant's insurance carrier and no medical or PSG contraindications to AutoPAP exist, participants will be allowed to waive their in-lab PAP titration and start AutoPAP therapy according to their PAP randomization assignment. Adherence of PAP therapy will be monitored by electronic downloads or datacards within the PAP machines.

6.6 Month 1 and Month 2 Follow-up Visits/Assessments

Group 1: 1 and 2 months following PAP initiation – *Group 1 subjects will have the option of doing their MONTH 2 assessment by phone or in person*

Group 2: 1 and 2 months following randomization – *Group 2 subjects will have the option of doing either of these assessments by phone or in person*

All randomized subjects will undergo the following assessments:

- 1) Focused medical and surgical history as it relates to MS, sleep, and cardiopulmonary history
- 2) Medication review
- 3) PAP compliance review (datacard assessment) for Group 1
- 4) Fatigue, insomnia, and sleepiness assessments (see 7.2)
- 5) AE/SAE review

6.7 Month 3 Visit with repeat Cognitive Testing

Group 1: 3 months after PAP initiation

Group 2: 3 months after randomization

All randomized subjects will undergo the following assessments:

- 1) Focused medical and surgical history as it relates to MS, sleep, and cardiopulmonary history
- 2) Medication review
- 3) PAP compliance review for Group 1
- 4) Fatigue, insomnia, and sleepiness assessments (see 7.2)

- 5) Pain, anxiety, and quality of life assessments (see 7.2)
- 6) AE/SAE review
- 7) Repeat neuropsychological testing (see 6.2)
- 8) PAP titration for group 2 (if applicable)*

* Group 2 subjects are encouraged to undergo PAP titration on the night of the Month 3 visit. If they agree to this approach, the PAP titration will be scheduled around the time of the Month 2 visit.

6.8 Post-Study Follow-up phone assessment for Group 2 (1 month after Month 3 visit)

Following the Month 3 visit (and once the PAP titration is complete) , for Group 2 subjects who still express a desire to proceed with PAP treatment, the study team will contact the subject and/or DME company (phone or email) to confirm that a PAP prescription has been faxed to the subject's designated DME company), and if applicable, that UM sleep clinic follow up has been made. Three phone contacts will be attempted. Any barriers to the PAP prescription process will be passed on to sleep clinic staff for appropriate action. If no clinic follow up has been scheduled per the subject's account (and the subject still desires a sleep clinic appointment), the study team will contact appropriate UM sleep clinic personnel to contact the subject.

SCHEDULE OF ACTIVITIES

Study Activity	Baseline Visit	Baseline PSG visit	Month 0	Month 1	Month 2	Month 3
Demographics	X					
Medical/Surgical History	X			X	X	X
Medication review	X			X	X	X
Height, weight, neck circumference	X					
EDSS self-report	X					
AE/SAE review	X			X	X	X
Baseline neuropsych testing (all subjects)	X					
Repeat neuropsychological testing (OSA subjects)						X
Baseline PSG (all subjects who do not have U-M PSG within the past year)		X				
Randomization (for subjects with OSA on baseline PSG)			X			
PAP titration/prescription for Group 1			X			
PAP compliance review for Group 1				X	X	X
Fatigue (FSS), insomnia (ISI), and sleepiness (ESS) surveys	X			X	X	X
PROMIS/NeuroQOL measures	X					X

7. ASSESSMENTS

7.1 Primary Endpoint Assessments

Cognitive performance (primary outcome measure of interest) will be assessed with formal neuropsychological testing (see section 6.2). Sleep apnea severity (primary predictor of interest) will be assessed with overnight polysomnography (see section 6.3).

7.2 Exploratory

Measures of sleep quality and sleep fragmentation, as well as Innovative PSG Signal Analysis Algorithms (secondary predictors of cognitive performance), will be assessed with overnight polysomnography (see section 6.3).

Epworth Sleepiness Scale (ESS): The ESS is an 8-item questionnaire that asks about the likelihood of dozing in variably sedentary situations.³¹ This commonly used measure of subjective sleepiness, or sleep propensity, is reliable, internally consistent, and validated against objective polysomnographic measures. A score ≥ 10 suggests excessive sleepiness.

Krupp's Fatigue Severity Scale (FSS): The FSS is a validated, 9-item instrument that measures the impact of fatigue on multiple outcomes, with a physical focus.³² Prior studies have shown acceptable internal consistency and stability over time, and sensitivity to change that correlates with the subject's clinical improvement. Many if not most past studies on MS-related fatigue have used the FSS.

Insomnia Severity Index (ISI): The Insomnia Severity Index (ISI) is a 7-item questionnaire with 5-point Likert scale responses designed to assess the nature, severity, and impact of insomnia in adults.³³ Scores of 15 or higher reflect moderate clinical insomnia.

Patient Reported Outcomes Measurement Information System (PROMIS)/Quality of Life in Neurological Disorders (NeuroQoL): The federally-funded Patient Reported Outcomes Measurement Information System (PROMIS) and Quality of Life in Neurological Disorders (NeuroQoL) are two integrated systems of highly reliable and responsive assessment tools that use modern measurement theory to assess patient-reported health related quality of life. Using validated item banks and standardized metrics, PROMIS and NeuroQoL reliably measure patient-reported outcome measures (PROM's) for clinical research. PROMIS and NeuroQoL measures, derived from large question banks, can be given as static short forms (typically 7-8 items in length). Measures can be used as primary or secondary endpoints in clinical studies that assess treatment effect for multiple symptoms including quality of life, pain, anxiety, fatigue and sleep quality (www.nihpromis.org/; www.neruoqol.org).

7.2.1 General Medical History

General medical history will be assessed at baseline and in all follow-up visits. Subjects will be queried about any chronic or ongoing health conditions that require treatment (which will be recorded in the CRF). Subjects will also be asked to provide their list of medications and allergies.

7.2.2 Concomitant Medication Use

Concomitant medications will be assessed at each visit and/or phone contact and recorded in the CRF.

7.2.3 Adverse Events

Adverse events will be assessed at each visit by questioning subjects about any symptoms they have been experiencing while on the study.

8. ADVERSE EVENT REPORTING

Multiple Sclerosis is a disease with many disease-related symptoms and complications, and there are many common mild side effects associated with PAP therapy. Due to the patient population and the nature of the disease, as well as the lack of experimental interventions in this study (only standard of care procedures and treatments will be used) we would like to implement the following AE/SAE collection/reporting guidelines:

SAE events that meet all 3 of the following criteria will be collected and submitted:

- Serious;
- Related; and
- Unanticipated

In addition, the following AEs will be collected and submitted:

- Any AE that results in a change to research

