PAP Therapy: There may be skin irritation related to the **PAP** mask, and masks can be uncomfortable and create a feeling of claustrophobia. There are multiple choices and sizes for sleep masks, and the provider will work with the subjects to find the most comfortable mask. There may be difficulty tolerating the forced air, but the pressure settings can be adjusted by working with the sleep machine provider. Subjects might experience a dry stuffy nose which can be treated with a saline nasal spray or humidified air that can be run through the PAP machine. The providers of these machines are very familiar with resolutions to and they will try and assist subjects in order to resolve any issues.

Confidentiality: The records of this study will remain confidential and protected; however, there is a risk for a breach of confidentiality. This risk is minimal, because a number of precautions have been taken in order to protect confidentiality. All data collected will be kept secure and in a locked office. Records will be coded and identifying information (such as name and registration numbers) will be removed and stored on a key in a separate location so that confidential information cannot be traced back to the subject. Only authorized members of the research team will have access to study records.

Standard care PAP treatment arm (for Group 2): Given that most consequences of OSA take months to years to manifest (cardiovascular disease, metabolic syndrome), we do not anticipate any significant long-term side effects from deferring PAP for 3 months for Group 2. Identification of sleep disordered breathing will be facilitated by enrollment into this study. Nonetheless, to avoid hazardous short-term consequences of OSA caused by excessive

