sleepiness (e.g., motor vehicle accidents), ESS scores ≥ 16 on baseline or follow-up visits will be cause for study exclusion/discontinuation. This cutoff was chosen based on data that demonstrate an ordinal increase in risk of sleepy driving accidents with increases in ESS score, particularly in subjects with ESS scores > 15 . We will also consider extreme OSA (RDI >60 respiratory events per hour, or unstable ECG rhythms on PSG) to be exclusionary, regardless of ESS score. For subjects who are not considered to be high risk per these criteria, we do not expect the risk of participating in this trial and having no CPAP for 3 months to exceed the risk encountered in routine clinical practice, as wait times for sleep clinic evaluations, subsequent sleep clinic referral, PSG, CPAP titration, and CPAP initiation at home currently often amount to 3 months or longer at U-M sleep clinics.

Alternative treatments and procedures: This study does not include an intervention. Therefore, there are no applicable alternative treatments or procedures.

As with any research study, there may be additional risks that are unforeseeable.

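### Under section 8, a foreseen sleepiness-related accident that does not change the research has no assured place in the safety data

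*Combined protocol and SAP*

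**What the plan says.** Section 8 sets one rule for both collecting and submitting: "SAE events that meet all 3 of the following criteria will be collected and submitted". The criteria are serious, related and "Unanticipated", joined by *and*. A second category follows directly: "Any AE that results in a change to research". The reasons given are that MS brings many symptoms of its own, that mild PAP side effects are common, and that "only standard of care procedures and treatments will be used".

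Section 7.2.3 is broader: "Adverse events will be assessed at each visit by questioning subjects about any symptoms they have been experiencing while on the study". Sections 6.6 and 6.7 and the Schedule of Activities place an AE/SAE review at Months 1, 2 and 3 for all randomized subjects.

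Section 1.3, in the paragraph on Group 2, names the hazard in one sentence, which begins "Nonetheless, to avoid hazardous short-term consequences of OSA caused by excessive" and continues "sleepiness (e.g., motor vehicle accidents), ESS scores ≥ 16 on baseline or follow-up visits will be cause for study exclusion/discontinuation". It goes on to say that subjects who are not high risk by the stated criteria should face no greater risk than in ordinary care, where waits for PAP are often three months or longer.

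**The concern.** The timing of PAP is assigned by randomization, so the three-month deferral in Group 2 is an exposure that the study assigns, and Group 1 is a concurrent comparator. The protocol names the short-term harm it has in mind. The collection rule then appears to leave that harm out, because an event named in advance is hard to call unanticipated.

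At stake is whether the trial can describe by arm the hazard it names, and whether it can check its own statement that deferral should carry no more risk than routine practice. The cognitive endpoints are not affected.

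**Working it through.** The plan states no figure on this point, so there is nothing to reproduce. The check sets the sections side by side, with a short illustration of scale.

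**1. Does the filter govern collection or only submission?** Both. Section 8 uses the two verbs together and requires all three criteria at once.

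**2. How would a serious sleepiness-related accident in Group 2 fare?**
- *Serious:* met by assumption.
- *Unanticipated:* the term is undefined. Section 1.3 names such accidents in advance, so on a plain reading the criterion fails.
- *Related:* this could fail too. Section 1.3 states that the study has no intervention, and section 8 rests the filter on the absence of anything experimental. A reader who accepts that would find nothing for the accident to be related to.
- *Change to research:* an accident that led to a change would be collected whatever its expectedness. The term is undefined. One possible link, discontinuation for sleepiness, is unsettled: section 1.3 applies ESS ≥ 16 at baseline or follow-up, while section 4.2 (criterion 14) and section 13 mention baseline only. Those sections must be reconciled.

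What remains is an accident that is foreseen and changes nothing in the research. Section 8 does not collect it.

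**3. Does another section recover it?**
- Section 7.2.3 has the question asked but does not say the answer is recorded. Sections 7.2.1 and 7.2.2, by contrast, say that history and medications go in the CRF.
- Section 7.2.1 covers chronic or ongoing conditions needing treatment. Some injuries would qualify; a crash without lasting injury would not.
- Section 10.1 has a sentence on reporting safety incidents, but it closes the paragraph on self-harm and defers to other protocols.
- Section 10.2 has the monitor review adverse events and subject records, which depends on what was recorded.
- Sections 9.2 and 9.3 contain no comparison or listing of harms by group.

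None of these clearly recovers the event.

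**4. What is captured?** The ESS is taken at baseline and Months 1, 2 and 3 in both groups. Its change is an exploratory endpoint (section 2.2.2) with a planned analysis (section 9.3). Sleepiness is therefore measured; accidents and other SAEs outside the filter are not.

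**5. Scale.** Group 2 has n ≈ 47 (section 5.1). The documents give no accident rate, so the three-month rates p below are assumptions. Expected events = 47p; chance of at least one = 1 − (1 − p)^47.

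| Assumed p | Expected events | Chance of at least one |
|---|---|---|
| 0.5% | 0.24 | 21% |
| 1% | 0.47 | 38% |
| 2% | 0.94 | 61% |
| 5% | 2.35 | 91% |

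For example, at 1%: 47 × 0.01 = 0.47, and 1 − 0.99^47 = 0.38. Over the lower three rates fewer than one event is expected, so a single uncollected accident could be the whole record. The same figures show that 47 patients cannot support a formal comparison, even with full collection.

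**The case against.** Limited collection is a deliberate choice with a stated reason, and the trial has no safety objective or endpoint. Adverse events are asked about at every visit, nothing says that events outside section 8 are discarded, and the ESS follows the mechanism of the foreseen harm in both arms. This stands in part. It makes the point a gap between sections 7.2.3 and 8, with no effect on the efficacy analysis. It does not close the gap: the stated reason concerns MS symptoms and common mild PAP effects, which is no ground for omitting crashes or other SAEs.

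A reader might infer several stronger things that the documents do not support:
- *That such accidents are barred outright, or recorded at zero by rule.* The change-to-research route exists, and the undefined third criterion leaves classification to judgement.
- *That unblinded investigators judge relatedness.* Section 5.2 leaves the PI and co-investigators unblinded, but no section says who makes this judgement.
- *That the protocol claims deferral is free of risk.* Its claim is relative to routine practice.
- *That an upper confidence limit from zero events in Group 2 measures the defect.* That limit would be the same with complete capture, and no such report is planned.

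**Conclusion.** The point holds in a limited form. On a plain reading of section 8 together with section 1.3, a serious sleepiness-related accident that was foreseen and does not change the research would not be collected, although the visits that could elicit it are already scheduled. The same applies to any other SAE judged anticipated or unrelated. As written, the trial cannot describe by arm the hazard it names, nor check its expectation about risk relative to routine practice.

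The conclusion rests on two readings: that an event named in the protocol is not unanticipated, and that collection in section 8 means entry into the study data. Its size cannot be fixed, because no event rate is given; under the assumed rates few events would occur, so each one matters to a descriptive account. No primary result depends on it. It is an inexpensive change that should be made.

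**What to change.** Reconcile sections 7.2.3 and 8 by separating collection from submission.

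- **Collect:** record in the CRF all SAEs in both arms, regardless of relatedness or expectedness, together with a short fixed list of sleepiness-related accidents or injuries. Use the AE/SAE reviews already set for Months 1, 2 and 3.
- **Submit:** keep the three-criterion filter for IRB submission only. Define the third criterion, and say what counts as a change to research.
- **Report:** add to section 9 a descriptive table of these events by arm, with no test. Record event dates and show follow-up time, because sections 6.6 and 6.7 count visits from PAP initiation in Group 1 and from randomization in Group 2.

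The cost is one CRF page and minor data entry at contacts that already take place. With about 47 deferred patients the table can only describe, and the report should say so. No clinical rule needs to change for this.

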9.0 DATA ANALYSIS/STATISTICAL METHODS

9.1 Sample Size Determination

Estimates (means and standard deviations) are derived from our recent data that evaluated SDMT scores among MS subjects referred for overnight PSG, and previously published interventional studies in that evaluated the effects of medical interventions on components of the MACFIMS in MS patients. We have chosen to focus on SDMT score as the primary outcome variable of interest, as the SDMT encompasses multiple domains of cognitive function, is frequently used in MS clinical studies as a reliable measure of cognitive impairment, and is sensitive to changes in intervention.

Based on a power analysis of two sample means (unequal sample sizes, with 2:1 randomization) with a 0.05 two-sided significance level, and an estimated S.D. of 9, a total sample size of 140 subjects will have an 86.3% power to detect a 5-point difference in SDMT score between groups, on month 3 testing, for hypothesis 2. Similarly, using individual MACFIMS components as outcome variables (in separate models), a multiple linear regression power analysis shows that a sample size of n=140 subjects will yield 88% power to detect an R-square difference of 0.05 for the test predictor of interest (% PAP use per month, as a continuous measure), assuming the R-squared explained by the adjustment variables is at least 0.3.

Although we predict a low dropout rate due to the short duration of the study, if we assume a dropout rate of 15% (10 dropouts per group), we will still have a power of 81.2% power to detect a 5-point difference in SDMT score between groups, on month 3 testing.

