Subjects who meet criteria for OSA on baseline or clinical in-lab PSG (n~140, anticipated) will then be randomized into one of two groups (2:1 randomization): immediate treatment with PAP (Group 1, n~93) followed by repeat neuropsychological testing at 3 months post-PAP; or standard of care application of PAP at 3 months post-randomization, after completion of repeat neuropsychological testing (Group 2, n~47). Analyses will focus on relationships between standard PSG measures (Respiratory Disturbance Index, oxygen desaturation index, and minimum oxygen saturation), innovative new quantitative PSG measures and MACFIMS scores, as well as mean changes from baseline in individual and composite MACFIMS scores following treatment with PAP therapy.

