9.2 Analysis of Primary Endpoint

Aim 1: Multivariate linear regression models will be used to analyze the effects of baseline PSG-derived standard measures of sleep disordered breathing (including RDI, ODI, minimum O2 saturation), on individual cognitive test scores (continuous outcome variables of interest, in separate models) for Aim 1, controlling for other sleep, serological, and clinical variables. Additional models that use computed respiratory cycle-related EEG changes (calculated as the maximum difference between the mean EEG powers associated with each of the 4 respiratory cycle segments as predictor variables) will be used to evaluate the effects of respiratory-related cortical microarousals on cognitive test scores, controlling for other clinical and sleep-related variables. Separate models that use computed temporal patterns of sleep stages as predictors of cognitive test scores will also be constructed.

Aim 2: Multivariate linear regression models will be used to test the effects of Group effect on 3-month (“post”) cognitive test scores, controlling for baseline (“pre”) test scores. We will also examine the association of PAP use as a continuous variable, based on mean nightly hours of use per month, on 3-month individual cognitive test scores, controlling for baseline scores. Separate models will be used for each cognitive test of interest. Predictor variables that are unbalanced between groups despite randomization will be used as covariates in the analyses.

To evaluate early effects of PAP therapy on cognitive scores, sleep stage dynamics will also be assessed during PAP titrations to determine whether changes in sleep stage stability predict improvements on cognitive test scores in separate models.

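### Section 9.1's power after dropout does not match its dropout pattern, and the PAP-use model in 9.2 cannot separate being in Group 1 from using PAP more

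*Combined protocol and SAP*

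**What the plan says.** Section 9.1 bases the sample size on the SDMT: two-sided 0.05, SD 9, a 5-point difference and 140 patients randomised 2:1, for 86.3% power. Sections 3 and 6.4 give the arms as about 93 (Group 1, expedited PAP) and 47 (Group 2, delayed PAP). On losses, 9.1 says "if we assume a dropout rate of 15% (10 dropouts per group), we will still have a power of 81.2% power".

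For PAP use as a predictor, 9.1 says that "a sample size of n=140 subjects will yield 88% power to detect an R-square difference of 0.05", provided the adjustment variables explain at least 0.3. It describes the predictor as a percentage: "PAP use per month, as a continuous measure". No power after dropout is given for this model.

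Section 9.2 describes the analysis itself: "We will also examine the association of PAP use as a continuous variable, based on mean nightly hours of use per month". The outcome is each month 3 test score, adjusted for its baseline value. Section 9.2 adds that predictors found unbalanced between groups become covariates. It states neither a Group term nor a restriction to Group 1, and does not say how Group 2 is coded.

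Group 2 receives "standard of care application of PAP at 3 months post-randomization, after completion of repeat neuropsychological testing" (section 3), with "delayed PAP titration after their month 3 cognitive testing" (section 6.4). Section 6.6 plans a "PAP compliance review (datacard assessment) for Group 1", and section 6.7 likewise limits the month 3 review to that group.

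**The concern.** There are two separate issues.

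First, the dropout sentence gives a percentage, a count per arm and a power, and they do not describe the same scenario. Under 2:1 allocation, equal counts lost from each arm are not equal percentages, and losses from the smaller arm cost more power.

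Second, a continuous PAP-use analysis placed beside the Group test would normally be read as a use-response analysis: among people given PAP, do those who use it more score better? With n=140 the model includes about 47 patients whose planned use is zero. Without a Group term, their difference from Group 1 enters the PAP-use coefficient. A significant result could then be reported as evidence that more use gives more benefit when it only restates the Group difference.

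**Working it through.** **1. Power for the Group comparison.** Inputs from 9.1: difference 5, SD 9, two-sided 0.05. Noncentrality = 5 / (9 × √(1/n1 + 1/n2)), with n1 + n2 − 2 degrees of freedom.

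| Group 1 / Group 2 | Noncentrality | t-test power | Normal approximation |
|---|---|---|---|
| 93 / 47 | 3.10 | 86.9% | 87.4% |
| 92 / 46 (exact 2:1) | 3.08 | 86.3% | 86.8% |
| 80 / 40 | 2.87 | 81.2% | 81.8% |
| 79 / 40 (15% lost per arm) | 2.86 | 81.0% | 81.7% |
| 83 / 37 (ten lost per arm) | 2.81 | 79.6% | 80.2% |

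The plan's 86.3% reproduces at 92/46 and its 81.2% at 80/40, so the method is the t-test with the 2:1 ratio kept. From 93/47, reaching 80/40 means 93 − 80 = 13 and 47 − 40 = 7 losses. Ten per group is 10/93 = 10.8% of Group 1, 10/47 = 21.3% of Group 2 and 20/140 = 14.3% overall.

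**2. The 88%.** With one tested term, f² = 0.05/(1 − 0.3) = 0.0714 and noncentrality = 140 × 0.0714 = 10.0. The noncentral F gives 88.1%, which reproduces the plan. The other common convention, f² = 0.05/(1 − 0.3 − 0.05) = 0.0769, gives 90.3%.

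**3. Size of the planned Group effect on the same scale.** With p = 93/140, p(1 − p) = 0.2230. Variance due to Group is 0.2230 × 5² = 5.575. R-square = 5.575/(81 + 5.575) = 0.064, against the 0.05 increment powered.

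**4. How much of that the PAP-use variable picks up.** Let Group 2 use be zero and Group 1 use have mean m and SD s. The share of the variance in use that lies between groups is (1 − p)m² / [(1 − p)m² + s²]. If there is a 5-point Group effect but no use-response, the pooled R-square for PAP use is 0.064 × this share. If everyone in Group 1 used PAP equally, the share would be 1 and the model would be the Group comparison. The documents give no adherence distribution, so the values below are assumptions. The significance rates come from 6,000 simulated trials per setting, with gamma-distributed use and adjustment R-square 0.3.

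| Assumed Group 1 use | Between-group share | Pooled R-square, no use-response | Pooled model significant |
|---|---|---|---|
| 3 h, SD 2.5 | 0.326 | 0.021 | 54% |
| 4 h, SD 2.5 | 0.462 | 0.030 | 70% |
| 5 h, SD 2 | 0.677 | 0.044 | 85% |

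With a Group term, or in Group 1 alone, the rate is 4–5%. The 54–85% is not a false-positive rate, because the Group effect in these trials is real. It shows only that the pooled test does not isolate use-response.

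**5. Power for use-response among PAP users.** Assume a constant slope and a pooled increment of 0.05. The within-Group-1 f² is then the pooled f² × s²/[p(1 − p)m² + ps²]. At n=93, under the two conventions of step 2, power is 73–76% (3 h, SD 2.5), 63–66% (4 h, SD 2.5) and 43–45% (5 h, SD 2). Putting n=93 into step 2 and carrying the 0.05 over unchanged gives 72–75%, but that ignores the change in the spread of use once the zero-use arm is removed.

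**The case against.** On dropout, the 81.2% agrees with the 15% in the same sentence: 15% lost from each arm gives 81.0%. Only the count in brackets is loose, the arm sizes are approximate, and the normal approximation still exceeds 80% for 83/37. The planned analysis also adjusts for baseline. If the baseline correlation were 0.3 (an assumption), 83/37 would give 83.2%. All of this stands. It makes the mismatch small but does not remove it.

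On PAP use, 9.1 states n=140 and 9.2 speaks only of an association. Neither claims power among PAP users. A reader might infer that the 88% is wrong, or that the sponsor offers it as use-response power. The documents support neither reading: the figure reproduces for a pooled model. A reader might also expect to replace it with 72–75%. That is not supported either, because it rests on an adherence spread that the documents do not give and lies near the top of the illustrative range.

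One could add that zero use in Group 2 is an inference. Section 4.1 admits people who have not used PAP compliantly, so some prior or incidental use is conceivable. But section 4.2 excludes current PAP treatment, and sections 3 and 6.4 put Group 2's PAP after month 3 testing, so planned use is zero.

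Finally, a power calculation in R-square terms does not depend on the unit of the predictor, so the metric mismatch leaves the 88% intact. That is true. But percentage use and nightly hours may be different variables, and only one can be the planned predictor.

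**Conclusion.** The point holds in a limited form and is minor.

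- **Dropout:** the stated power and the stated count per group disagree by 1.6 points (81.2% against 79.6% by t-test). This rests only on figures in the plan.
- **PAP-use model:** as written, it mixes the randomised Group contrast with adherence, which is not randomised. This follows from the n of 140, the absence of a stated Group term and Group 2's delayed start. How strongly the two are mixed depends on the spread of use in Group 1, which the plan does not give.
- **The 88%:** valid for the pooled model. Power for use-response among PAP users is expected to be lower, but no single figure can be derived from the documents.
- **Metric:** 9.1 and 9.2 name different measures of PAP use.

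A reader might infer that the trial is underpowered or that its main result is at risk. It is not: the randomised Group comparison and the sample size are untouched.

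**What to change.** In 9.1, restate the dropout scenario as either about 15% in each group (about 13–14 and 7 dropouts) with about 81% power, or ten per group with 79.6%. Label the 88% as applying to the pooled model with n=140. Add that power for use-response among PAP users is expected to be lower and depends on the spread of use. Do not insert a specific figure.

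In 9.2, keep the pooled association under that name and state how Group 2 is coded. Add a model with a Group term, or one within Group 1, for use-response, and say that its slope is observational because adherence is not randomised. Name one PAP-use metric and use it in both sections.

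The cost is a few sentences and one model term, plus accepting lower power for a supportive analysis. No new data are needed, and neither the sample size nor the primary Group comparison changes.
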